15.2 Size/Accrual Rate

The sample size is 34 patients. The planned accrual rate is 2-3 patients per month. Therefore, accrual is expected to be complete in no more than 17 months. Assuming patients continue treatment for up to 1 year (12 months) and allowing 6 months for quality assurance, the anticipated duration of the study is approximately 35 months.

15.3 Stratification Factors

There are no prespecified stratification factors for the primary endpoint.

15.4 Analysis of Secondary Endpoints

Safety Lead-In: A safety lead-in will be conducted as described in Section 4.2. A summary of the adverse events and any DLT observed during the safety lead-in phase will be provided, as well as the study team's assessment of whether the protocol-specified dose and schedule is tolerable.

Adverse event rates: Adverse events will be recorded at each clinical visit and will be categorized according to NCI CTCAE version 4.0. Adverse event rates will be reported as counts and percentages per adverse event basis by grade.

Overall survival and progression free survival: Overall survival is defined as the time from the date of first treatment with study drug to the time of death from any cause or last follow-up if alive. Progression free survival is defined as the time from first treatment with the study drug to the earliest of either disease progression or death from any cause. Patients who are alive and progression free will be censored at the time of their last follow-up. The Kaplan-Meir method

will be used to evaluate all time to event endpoints. Median overall survival and median progression free survival will be reported with 95% confidence intervals.

Response rate: Patient responses will be evaluated according to RECIST version 1.1 as described in section 12. The response rate is defined as the number of patients having a best objective tumor status of complete response or partial response lasting at least four weeks divided by the number of evaluable patients. The response rate will be reported with 95% confidence intervals.

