As of October 31st, 2020, there have been no deaths with in 30 days of treatment with ATX-101. In general treatment has been well tolerated with patients discontinuing treatment with ATX-101 as a consequence of disease progression rather than toxicity. No ATX-101 related grade 3 or higher adverse events (AEs) or serious adverse events (SAEs) have been reported during the entire study duration. No dose limiting toxicity (DLT) has been observed. The most frequently observed ATX-101 related AEs were infusion related reaction. Grade 1 infusion reactions were reported in 13/21 patients and grade 2 infusion reactions were reported in 14/21 patients over the entire duration in all patients. Reported infusion reactions included itchiness, redness, urticaria, fever, rash, swelling, flushing, hives and confusion. Infusion reactions occurred during the first but also during later infusions and resolved completely after ATX-101 infusion interruption and/or treatment with corticosteroids and/or antihistamines. In the majority of patients, the infusion of ATX-101was safely restarted and treatment was completed. So far, there is no evidence for a dose relationship of infusion reactions. The mandatory premedications consisted of dexamethasone, histamine 1 and 2 receptor antagonists, acetaminophen and montelukast. Besides, infusion reactions, ATX-101 related AEs reported at least twice during the entire study duration were fatigue (6 times), diarrhea (3 times) and dysgeusia (2 times). All of these were grade 1 in severity with the exception of 2x fatigue which were grade 2. The table below reports all the adverse events observed in these 21 patients until October 31st, 2020.

Event (Preferred Term)	Cohort 1 20 mg/m ² (n=8)	Cohort 2 30 mg/m ² (n=3)	Cohort 3 45 mg/m ² (n=4)	Cohort 4 60 mg/m ² (n=6)
Grade 1: mild	4 (50%)	3 (100%)	4 (100%)	4 (66.7%)
Grade 2: moderate	2 (25%)	1 (33.3%)	3 (75%)	5 (83.3%)
Grade 3: severe	0	0	0	0
Grade 4: life threatening	0	0	0	0

Treatment related treatment emergent adverse events observed in study AM ATX101-01 (31 October 2020) – Number (%) of patients experiencing an adverse event, by dose level.

Treatment related treatment emergent adverse events observed at least twice in study AM ATX101-
01 (31 October 2020) – Total number of events experienced by all patients on the study

Event (Preferred Term)	Grade 1	Grade 2	Grade 3	Grade 4
Infusion related reaction	13	14	0	0
Fatigue	4	2	0	0
Infusion site conditions*	3	2	0	0
Dysgeusia	3	0	0	0

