7.4 Duration of Follow Up

Patients who do not progress while on study treatment will be followed every 3 months after completion of study treatment for the first 12 months and then every 6 months thereafter for both survival and disease status until death or for a period of at least 3 years, whichever comes first.

For patients who end study treatment due to progression, information on survival will also be collected every 3 months after completion of study treatment for the first 12 months of follow up and then every 6 months until death or for a period of at least 3 years, whichever comes first.

Patients removed from study for unacceptable adverse events will also be followed for information on resolution or stabilization of the adverse event.

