8. DOSING DELAYS/DOSE MODIFICATIONS

The following guidelines should be observed:

- If a patient experiences multiple adverse events and there are conflicting recommendations as to management, the investigator should use the recommended dose adjustment that reduces the dose to the lowest level of the available options.
- Any patient who requires a delay in therapy exceeding 28 days for treatment-related adverse events should be removed from the study. Any patient who requires more than three dose reductions should also be removed from the study.
- Patients should receive all relevant supportive care during the study, including, but not limited to: blood product support, antibiotic treatment, and management of other newly diagnosed medical conditions. All blood products and concomitant medications (such as antiemetics, analgesics, antidiarrheals) received from the first day of study drug treatment until 30 days after the final dose of study drug treatment must be recorded.
- Patients who require radiation therapy while on study must be removed from the study.
- Patients who require surgery while on study may proceed with surgery provided resection or removal of sarcoma is not part of the surgery. However, if a dose delay of more than 28 days is required, the patient must be removed from the study.
- Blood products and growth factors should be used as clinically warranted and in accordance with institutional policy. The use of prophylactic filgrastim and related medications to avoid dose reductions or delays is discouraged. The use of these agents in the setting of complications from therapy, such as severe infection, is permitted and must be documented.

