11. STUDY CALENDAR

CBC w/differential (1,3)*	Х	Х	Х	Х	Х		Х		Х
Comprehensive metabolic panel (1,3,4)*	Х	Х	Х	Х	Х		Х		Х
Serum or urine pregnancy test (1, 3)	Х								Х
Urinalysis (1, 3)	Х						Х		Х
CT or MRI of chest, abdomen, pelvis (2)	Х						Х		Х
Tumor biopsy for correlative studies (5)	Х				X				
Follow-up telephone contact (6)	llow-up telephone contact (6)				Х				
*Clinical/laboratory safety assessm	ents must	be con	nple	ted w	ithin 24	4 hours	prior to	treatmen	t.

(1) Screening procedures must be completed within 21 days of initiating study treatment, with the exception of the serum or urine pregnancy test, which must be completed within 7 days of initiating study treatment. Protocol-specified screening procedures that are performed as part of standard of care and are within the specified timeframes may be used for screening purposes.

(2) Baseline imaging can include either (a) CT, spiral CT or MRI, or (b) FDG-PET with diagnostic CT performed with IV and oral contrast and CT acquired with 5 mm or less slice thickness. Imaging studies used for baseline tumor measurements must be performed within 21 days of initiating study treatment. Imaging studies are performed every 2 cycles (6 weeks, 42 days) for the first 36 weeks of study treatment, and then every 3 cycles (9 weeks, 63 days) thereafter. Imaging studies may be performed +/- 5 days from the required date. In the event of dose delays/holds, imaging studies should still be obtained at the scheduled timepoints as measured from cycle 1 day 1, without delays to account for dose delays/holds. Confirmatory scans must be obtained at least 4 weeks after the documentation of an objective response. It is acceptable to perform confirmatory assessments at the next appointed evaluation per protocol. Response assessment should include assessment of all sites of disease and use the same imaging method as used at baseline whenever possible.

(3) All laboratory studies may be performed +/- 3 days from the required date. Local laboratory testing is permitted, except for the serum/urine pregnancy test.

(4) Comprehensive metabolic panel includes albumin, alkaline phosphatase, total bilirubin, bicarbonate, blood urea nitrogen, calcium, chloride, creatinine, glucose, potassium, total protein, AST, ALT and sodium.

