(5) The first 10 patients enrolled on the study will undergo paired pre-treatment and on-treatment biopsies. The baseline biopsy specimen must be obtained within 21 days of cycle 1 day 1, provided consent is obtained and other eligibility criteria are met. The on-treatment biopsy specimen will be performed cycle 2, days 1 or 2. Biopsies will be obtained from the same anatomic site of disease whenever possible.

(6) A post-study follow-up contact via telephone by research staff will be conducted every 3 months during the first year after the end of study participation, and then every 6 months thereafter. Information is obtained on disease status, survival status, and new anti-cancer therapy received. Follow-up continues for at least 3 years as measured from the date of study registration or until death, whichever comes first.

(7) The end-of-study visit must be scheduled within 28 days after the last dose of study drug (+/-7 days) and before starting any new anti-neoplastic therapy.

(8) Clinical assessments will occur on days 1, 8 and 15 of cycle 1, and then on day 1 of all cycles thereafter. Clinical assessments may occur +/- 3 days from the planned date but must occur within 24 hours of ATX-101 administration.

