12. MEASUREMENT OF EFFECT

12.1 Antitumor Effect – Solid Tumors

For the purposes of this study, patients will be re-evaluated for response every 6 weeks. In addition to a baseline scan, confirmatory scans should also be obtained 4 weeks following initial documentation of objective response.

Response and progression will be evaluated in this study using the new international criteria proposed by the revised Response Evaluation Criteria in Solid Tumors (RECIST) guideline (version 1.1). Changes in the largest diameter (unidimensional measurement) of the tumor lesions and the shortest diameter in the case of malignant lymph nodes are used in the RECIST criteria.

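### PFS is censored at last follow-up rather than at the last tumour assessment, so median PFS can be slightly overstated (minor)

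*Combined protocol and SAP*

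**What the plan says.** Section 15.4 defines PFS from first treatment to progression or death from any cause, to be summarised by a Kaplan-Meier median with a 95% confidence interval. Its censoring rule is: "Patients who are alive and progression free will be censored at the time of their last follow-up". Section 12.6 repeats the definition without a censoring rule. Section 12.1 supplies the progression criteria, RECIST 1.1: "Response and progression will be evaluated in this study using the new international criteria".

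The scan schedule is in Section 11, footnote 2: "Imaging studies are performed every 2 cycles (6 weeks, 42 days) for the first 36 weeks of study treatment", then every 9 weeks. The calendar table is damaged in the text available, but appears to add a scan at end of treatment. After that, footnote 6 provides: "A post-study follow-up contact via telephone by research staff will be conducted every 3 months" in the first year, then every 6 months. At these contacts "Information is obtained on disease status, survival status, and new anti-cancer therapy received". Section 7.4 follows patients who stopped without progression every 3 months for a year and then "every 6 months thereafter for both survival and disease status until death", or for at least 3 years. Neither place schedules a scan.

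Patients can leave treatment without documented progression. Section 7.3 lists adverse events, intercurrent illness and the patient's decision. Section 8 adds, for example: "Patients who require radiation therapy while on study must be removed from the study".

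**The concern.** A censoring time should be the last time at which the patient was known to be free of the event. For PFS judged by RECIST, that is the last adequate tumour assessment. Under 15.4 the clock can run to a later contact at which no tumour was measured.

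Take a patient who stops at month 2 with a clean scan and is alive, with no progression reported, at the call 12 months later. Under 15.4 this patient is censored at 2 + 12 = 14 months. Censoring at the last scan gives 2 months. The 12-month difference is unverified, and it keeps the patient in the Kaplan-Meier risk set while others progress.

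Median PFS is a named secondary endpoint (Section 2.2.3). It will be read beside the 1.5 to 4.2 month medians quoted in Section 15.1, and a single-arm trial has no control arm that would share the bias.

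**Working it through.** **1. What does not depend on the rule.** The trial's decision uses a binomial count of patients progression free at 12 weeks: continue if at least 4 of 10, promising if at least 15 of 34. With X1 ~ Bin(10, p) and X2 ~ Bin(24, p), the probability of success is the sum over x = 4 to 10 of P(X1 = x) × P(X2 ≥ 15 − x). At p = 0.30 this is 0.0456 and at p = 0.55 it is 0.853, which reproduces the stated 0.05 and 85%. PFS censoring does not enter.

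**2. Direction.** The Kaplan-Meier estimate is the product of (1 − d/n) over event times. Keeping a patient in n whose progression would not be seen leaves d unchanged and raises each factor. The curve, and so the median, can only move up.

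**3. Size, large sample (400,000 patients per cell).**
- From the documents: true medians of 2.6 and 4.2 months (Section 15.1); calls at 3, 6, 9 and 12 months after exit, then every 6 months; follow-up to month 36.
- Assumed: exponential PFS with hazard λ = ln 2 / median; exits unrelated to prognosis with hazard λp/(1 − p), where p is the share leaving before progression; a scan at exit; median survival of 12 months after exit; calls that detect nothing.

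Medians in months:

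| True median | Rule | p = 5% | 10% | 20% |
|---|---|---|---|---|
| 2.6 | scans continued | 2.59 | 2.57 | 2.55 |
| 2.6 | 15.4 as written | 2.64 | 2.70 | 2.83 |
| 2.6 | last scan, all deaths as events | 2.64 | 2.68 | 2.78 |
| 4.2 | scans continued | 4.17 | 4.14 | 4.09 |
| 4.2 | 15.4 as written | 4.26 | 4.32 | 4.49 |
| 4.2 | last scan, all deaths as events | 4.25 | 4.29 | 4.42 |

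Excess as written over continued scanning: 0.05, 0.13, 0.28 (true 2.6) and 0.09, 0.18, 0.40 (true 4.2). An independent rerun agreed to about 0.02 to 0.04 month.

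**4. Size at n = 34** (4,000 trials per cell; progression dated at the next scheduled scan). The exit shares correspond to 34p = 1.7, 3.4 and 6.8 patients.
- No detection by telephone: mean excess 0.06, 0.12, 0.27 (true 2.6) and 0.08, 0.18, 0.41 (true 4.2).
- The median was identical to that under continued scanning in 95, 90 and 75% of trials (2.6) and in 94, 86 and 68% (4.2).
- The standard deviation of the median is about 0.7 (2.6) and 1.0 to 1.1 (4.2).
- Perfect detection by telephone, 4.2 case: mean excess about 0.03, 0.06, 0.11.
- In the large-sample 2.6 case with 20% exits, perfect calls do not help: the median is 2.84, because the first call comes 3 months after exit.

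**5. Cross-check.** A second simulation used medians of 6.9 and 13.9 weeks, which are 12 × ln 2 / −ln(0.30) and 12 × ln 2 / −ln(0.55), with 500 trials of 34 patients. At 10 to 20% exits the mean excess over continued scanning was 0.2 to 1.3 weeks, or 0.05 to 0.30 month at 4.35 weeks per month. At 30% exits it was 0.9 to 2.7 weeks, so describing the effect as slight depends on exits staying at or below about 20%.

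**6. What the recommended rule gains.** With no detection, the third row for each median in the table is the recommended rule under follow-up to month 36. Against 15.4 it gains 0.00, 0.02, 0.05 (2.6) and 0.01, 0.03, 0.07 (4.2), because most deaths after exit have by then become events. With an early data cut-off, 20% exits and no detection, the mean bias at n = 34 fell from 0.40 to 0.09 month. It was at or below that of the present rule in every n = 34 cell run with an administrative cut-off. Root-mean-square error was slightly higher in some cells with perfect calls.

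**The case against.** The best case for leaving 15.4 alone has four parts.

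- **Some progression will be picked up after treatment.** Section 12.4.3 asks that objective progression be sought even after stopping for deterioration, and 7.4 follows disease status without limiting this to telephone. 15.4 does not define last follow-up as a telephone call. This stands as mitigation. It does not supply scheduled scans or tie the censoring date to one.
- **Exits may be few.** Section 3.2 reports "patients discontinuing treatment with ATX-101 as a consequence of disease progression rather than toxicity". This stands, and points to the low end of the range.
- **The effect is small.** It is below sampling error, and no test or decision uses median PFS. This stands and sets the severity.
- **A stricter rule can do harm.** A reader might infer that PFS should count only RECIST progression and should censor deaths after two or more missed assessments. The documents do not support that as the main analysis. Sections 15.4 and 12.6 make death an event, and 7.3 recognises clinical progression as a reason to stop. If 5 to 20% of progressions are clinical only (assumed), the stricter rule lifts the median to about 2.7 to 3.2 months (true 2.6) and 4.4 to 5.1 (true 4.2), generally more than the bias being removed. With perfect calls in the 4.2 case at n = 34, its bias is about 0.09, 0.13, 0.14, against 0.03, 0.06, 0.11 under 15.4.

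**Conclusion.** The point holds as a minor one. 15.4 states a PFS censoring rule that can count unscanned time as progression free. The average overstatement at n = 34 is about 0.03 to 0.4 month for 5 to 20% exits, and in most simulated trials the median does not move. The result rests on assumed exit shares, exponential times, the assumed survival after exit, and exits unrelated to prognosis. If exits do worse (20% exits, progression hazard doubled, median survival 6 months), the 2.6 case gives 2.75 as written against a reference of 2.40, an excess of 0.35. Even the stricter rule then gives 2.52, leaving 0.12.

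A reader might infer that the efficacy conclusion is compromised. It is not: the decision rests on the 12-week count. Nor do the documents leave progression undefined, since 12.1 sets RECIST 1.1. What they leave open is the PFS censoring date and whether clinical or reported progression counts as an event.

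**What to change.** Amend Section 15.4 as follows.

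1. Apply last-contact censoring to overall survival only.
2. For PFS, censor patients alive without an event at their last adequate tumour assessment, or at first dose if there is none.
3. Keep death from any cause as an event. State that documented clinical or reported progression counts as progression on its documented date.
4. Report three sensitivity analyses: RECIST-only progression; censoring of progression or death that follows two or more missed assessments; and the present last-follow-up rule. For the second, say how assessments are counted after treatment, when none is scheduled, for example by running the footnote 2 schedule on from cycle 1 day 1.

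The cost is a few sentences, with no new visit, scan or form, because scan, contact and death dates are already collected. The downsides are slightly shorter PFS follow-up, little or no gain (and in some cases slightly more variability) when calls detect progression or follow-up is long, and residual bias if stopping is related to prognosis.

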15.5 Analysis of Correlative Science Endpoints

Analysis of correlative endpoints will be considered exploratory and hypothesis generating.

15.6 Reporting and Exclusions

15.6.1 Evaluation of toxicity

All patients will be evaluable for toxicity from the time of their first treatment with ATX-101. The safety population will consist of all patients who received at least one dose of study drug.

15.6.2 Evaluation of response

All patients included in the study who receive at least one treatment with the study drug will be assessed for response to treatment, even if there are major protocol deviations or if they are ultimately deemed ineligible. Each patient will be assigned one of the following categories: 1) complete response, 2) partial response, 3) stable disease, 4) progressive disease, 5) early death from malignant disease, 6) early death from toxicity, 7) early death from other cause, or 9) unknown (not assessable or insufficient data).

16. **PROTECTION OF HUMAN SUBJECTS**

This study is to be conducted in accordance with applicable government regulations and Institutional research policies and procedures.

This protocol and any amendments will be submitted to a properly constituted Institutional Review Board (IRB), in agreement with local legal prescriptions, for formal approval of the study conduct. The decision of the IRB concerning the conduct of the study will be made in writing to the investigator and a copy of this decision will be obtained before commencement of this study.

All subjects for this study will be provided a consent form describing this study and providing sufficient information for subjects to make an informed decision about their participation in this study. This consent form will be submitted with the protocol for review and approval by the IRB for the study. The formal consent of a subject, using the IRB-approved consent form, must be obtained before that subject is submitted to any study procedure. This consent form must be signed by the subject or legally acceptable surrogate, as outlined in the IRB approved protocol, and the investigator-designated research professional obtaining the consent.

17. STUDY FINANCES

17.1 Conflict of Interest

Any investigator who has a conflict of interest with this study (patent ownership, royalties, or financial gain greater than the minimum allowable by their institution, etc.) must have the conflict reviewed by the Columbia University Conflict of Interest Committee with a Committee-sanctioned conflict management plan that has been reviewed and approved prior to participation in this study. All CUMC investigators will follow the University conflict of interest policy.

17.2 Subject Stipends or Payments

No stipends or payments will be given to subjects.

18. PUBLICATION PLAN

Neither the complete nor any part of the results of the study carried out under this protocol, nor any of the information provided by the sponsor for the purposes of performing the study, will be published or passed on to any third party without the consent of the study sponsor. Any investigator involved with this study is obligated to provide the sponsor with complete test results and all data derived from the study.

